**Table 3: Table of Events (Continued)**

|  | Screening Period | Double-blind Treatment Period |            |            |                 |            |            |            |            |            |            |            |            |            |                 | Follow-up Period |  |
|--|------------------|-------------------------------|------------|------------|-----------------|------------|------------|------------|------------|------------|------------|------------|------------|------------|-----------------|------------------|--|
| Visit Number   | 1 Screening      | 2 Baseline                    | 3          | 4          | 5               | 6          | 7          | 8          | 9          | 10         | 11         | 12         | 13         | 14         | 15              | ET a  | 16 b                              |
| Week   | -4               | 0                             | 4          | 8          | 12 c | 16         | 20         | 24         | 28         | 32         | 36         | 40         | 44         | 48         | 52 d | NA               | Follow-up                                    |
| (Visit Window)   | 28 days          |                               | (± 3 days) | (± 3 days) | (± 3 days)      | (± 3 days) | (± 3 days) | (± 3 days) | (± 3 days) | (± 3 days) | (± 3 days) | (± 3 days) | (± 3 days) | (± 3 days) | (± 3 days)      | NA               | 4 weeks after the last dose of IP (± 3 days) |
| Stool Assessment   | X                | -                             | -          | -          | -               | -          | -          | -          | -          | -          | -          | -          | -          | -          | -               | -                | -  |
| Clinical Lab (Hematology) g   | X                | X                             | X          | X          | X               | X          | X          | X          | X          | X          | X          | X          | X          | X          | X               | X                | X  |
| Clinical Lab (Coagulation) g  | X                | X                             | -          | -          | X               | -          | X          | -          | X          | -          | X          | -          | X          | -          | X               | X                | X  |
| Clinical Lab (Chemistry) g  | X                | X                             | -          | -          | X               | -          | X          | -          | X          | -          | X          | -          | X          | -          | X               | X                | X  |
| Clinical Lab (Urinalysis) g   | X                | X                             | -          | -          | X               | -          | X          | -          | X          | -          | X          | -          | X          | -          | X               | X                | X  |
| Efficacy Assessments  |                  |                               |            |            |                 |            |            |            |            |            |            |            |            |            |                 |                  |  |
| Subject Diary h
Instruct use of electronic device/assess compliance | X                | X                             | X          | X          | X               | X          | X          | X          | X          | X          | X          | X          | X          | X          | X               | X                | X  |
| CDAI i  | X i   | X                             | X          | X          | X               | X          | X          | X          | X          | X          | X          | X          | X          | X          | X               | X                | X  |
| Ileocolonoscopy j   | X                | -                             | -          | -          | X               | -          | -          | -          | -          | -          | -          | -          | -          | -          | X               | X                | -  |

**Table 3: Table of Events (Continued)**

|                | Screening Period | Double-blind Treatment Period |            |            |                 |            |            |            |            |            |            |            |            |            |                 | Follow-up Period |  |
|----------------|------------------|-------------------------------|------------|------------|-----------------|------------|------------|------------|------------|------------|------------|------------|------------|------------|-----------------|------------------|--|
| Visit Number   | 1 Screening      | 2 Baseline                    | 3          | 4          | 5               | 6          | 7          | 8          | 9          | 10         | 11         | 12         | 13         | 14         | 15              | ET a  | 16 b                              |
| Week           | -4               | 0                             | 4          | 8          | 12 c | 16         | 20         | 24         | 28         | 32         | 36         | 40         | 44         | 48         | 52 d | NA               | Follow-up                                    |
| (Visit Window) | 28 days          |                               | (± 3 days) | (± 3 days) | (± 3 days)      | (± 3 days) | (± 3 days) | (± 3 days) | (± 3 days) | (± 3 days) | (± 3 days) | (± 3 days) | (± 3 days) | (± 3 days) | (± 3 days)      | NA               | 4 weeks after the last dose of IP (± 3 days) |

**Dosing**

|                     |   |   |   |   |   |   |   |   |   |   |   |   |   |   |   |   |   |   |
|---------------------|---|---|---|---|---|---|---|---|---|---|---|---|---|---|---|---|---|---|
| Dispense IP         | - | X | X | X | X | X | X | X | X | X | X | X | X | X | X | - | - | - |
| Return and Count IP | - | - | X | X | X | X | X | X | X | X | X | X | X | X | X | X | X |   |

CDAI = Crohn's Disease Activity Index; ECG = Electrocardiogram; ET = Early Termination Visit; ; FCBP = females of childbearing potential; ; IP = investigational product; NA = not applicable; ; Sc= Screening; ; V1 = Visit 1;

a Subjects who prematurely discontinue from the study at any time other than the Week 12 Visit and prior to the last scheduled study visit, including subjects who enter the Long-term Active-treatment Study (GED-0301-CD-004), will complete the Early Termination (ET) Visit (Section 6.3). The ET Visit should be completed as soon as possible after the decision is made to permanently discontinue the study treatment. Subjects who discontinue from the study at Week 12 will complete the Week 12 Visit.  
b Subjects who complete the Week 52 Visit, as well as subjects who prematurely discontinue from the study, will have a 4-week Follow-up Visit (Section 6.4). If the ET Visit occurs ≥ 28 days after the last dose of IP, then the Follow-up Visit is not required. Subjects entering the Long-term Extension Study will not have the Follow-up Visit.

- c At the Week 12 Visit and thereafter, until the Week 52 Visit, subjects [REDACTED], will be eligible to early escape into the Long-term Active-treatment Study (GED-0301-CD-004), or may discontinue from the study. In order to be considered for the early escape at [REDACTED]. Due to the delay in receiving the hematocrit sample results, beginning at the Week 12 Visit, and throughout the remainder of the study, the CDAI score will be evaluated by the site using the hematocrit results from the previous visit.
- d Subjects who complete the GED-0301-CD-002 study at the Week 52 Visit, will have the option to enter the Long-term Active-treatment Study. Subjects entering the Long-term Extension Study will not have the Follow-up Visit.
- e Pregnancy testing will be performed for FCBPs. Serum pregnancy tests will be performed at screening and urine pregnancy will be done at the remaining visits as described in Table 3.
- f Contraception education is for Females of Child Bearing Potential (FCBP). The Investigator will educate all FCBP about the different options of contraceptive methods and their correct use at Screening and Baseline Visits. The subject will be re-educated every time her contraceptive measures/methods or ability to become pregnant changes. The female subject's chosen form of contraception must be effective by the time the female subject is randomized into the study (for example, hormonal contraception should be initiated at least 28 days before baseline).
- g Details pertaining to clinical labs are provided in Section 6.5.3.
- h The electronic Subject Daily Diary (Section 6.6.1) will be provided to subjects at the Screening Visit. Subject compliance with the completion of diary data should be assessed at each study visit during the Screening and Double-blind Treatment Period.
- i The screening CDAI (Section 6.6.2) will be based on the Subject Daily Diary data collected during the Screening Period. Note that an abdominal exam is needed for CDAI assessment.
- j The screening ileocolonoscopy should be performed following confirmation of the subject's eligibility, based on the CDAI score. Follow-up ileocolonoscopies will be done at Week 12 and Week 52 (Section 6.6.5). The ET ileocolonoscopy will not be repeated if performed within 8 weeks of the previous ileocolonoscopy.
- [REDACTED]

## 6. PROCEDURES

The following procedures/assessments will be conducted according to the schedule indicated in the Table of Events (Table 3).

### 6.1. Screening Period

Screening evaluations will be performed for all subjects to determine study eligibility. These evaluations must be completed within 28 days prior to the date of the first dose of IP (study randomization) unless noted otherwise below. Subjects may be allowed to re-screen with approval from the sponsor or designee.

#### 6.1.1. Screening Visit

The following assessments will be performed at the Screening Visit as specified in Table 3, after informed consent has been obtained:

- Demographics including initials, date of birth, sex, race, and ethnicity-if allowed by local regulations
- Complete medical history including all relevant medical conditions diagnosed, and occurring prior to the Screening Visit, should be recorded.
- Prior and concomitant procedures including all procedures occurring  $\leq 30$  days before the Screening Visit
- Prior and concomitant medication evaluation including all medications (prescription and nonprescription, including vitamins) taken by the subject up to  $\leq 30$  days prior to the Screening Visit should be recorded. All medications taken by the subject at any time during the study must also be recorded. Other key medications and therapies, such as previous treatment for tuberculosis or relevant diseases, should also be recorded.
- Prior and concomitant CD medications taken by the subject and CD-related procedures performed, at any time prior to and during the study, should be recorded, including the stop dates for medications prohibited in the study.
- Adverse event assessment begins when the subject signs the informed consent form and is assessed continuously throughout the study, until 28 days following the last dose of IP. Refer to Section 10 for details pertaining to AEs.
- Pregnancy test is required for all female subjects of childbearing potential. Serum beta human chorionic gonadotropin  $\beta$ -hCG pregnancy test will be performed at the Screening Visit.
- Contraception education (Section 6.5.6)
- Vital signs including blood pressure, temperature, and heart rate
- Height and weight will be measured and recorded at screening; weight is to be done in street clothes, no shoes

- Complete physical examination (Section 6.5.1)
- 12-lead electrocardiogram (ECG) (Section 6.5.2)
- Stool culture analysis and assessment of Clostridium (C.) difficile toxin will be performed at the Screening Visit. Subjects with stool that is positive for any enteric pathogen or C. difficile toxin at the Screening Visit will be excluded from the study. Subjects who are initially positive for C. difficile toxin may re-screen for the study 8 weeks after the start of therapy, provided that the toxin results for C. difficile are negative (Section 6.5.4).
- Clinical laboratory evaluations will be performed by a central laboratory and are described below. Subject eligibility and clinical laboratory criteria are provided in Section 4.2. One laboratory re-test is allowed after obtaining Medical Monitor approval during the Screening Period. Details pertaining to the central laboratory assessments and panels are included in Section 6.5.3:
  - Hematology panel
  - Chemistry panel
  - Coagulation: prothrombin time (PT), activated partial thromboplastin time (APTT)
  - Urinalysis (dipstick)
    - Microscopic urinalysis (epithelial cells, red blood cells [RBC], white blood cells [WBC], crystals, bacteria, and casts) will be performed only if the dipstick urinalysis is abnormal.
- Subject Daily Diary (Section 6.6.1)
  - The electronic device to record the Subject Daily Diary [REDACTED] will be provided to subjects at the Screening Visit. Subjects should enter diary data continuously throughout the study.
- Subjects will receive instructions pertaining to the use of the electronic device and the importance of diary compliance throughout the study.
  - Diary compliance must be assessed throughout the study.

During the Screening Period, the following assessments and procedures will be performed following the Screening Visit and prior to study randomization as specified in the Table of Events (Table 3):

- To be eligible for the study, the subject must have a 7-day average stool frequency score  $\geq 3.5$  or a 7-day average an abdominal pain score  $\geq 1.5$  extracted from the subject daily diary, during the Screening Period.
- CDAI score (Section 6.6.2)
  - The CDAI score is a key efficacy assessment in this study and will also be used to determine study eligibility. The subject self-assessment questionnaire items that are included in the CDAI scoring will be extracted from the Subject Daily Diary.

- The screening CDAI score will be based on subject diaries collected during the Screening Period. If the screening CDAI score is  $\geq 220$  and  $\leq 450$ , the subject will proceed with the screening endoscopy.
- Ileocolonoscopy is the type of endoscopy being performed during this study (Section 6.6.5) and the SES-CD is the instrument being used to assess endoscopy (Section 6.6.6).
  - The screening endoscopy should be performed after confirmation of a qualifying CDAI score and a qualifying 7-day average of stool frequency or abdominal pain.
  - The SES-CD is a key efficacy assessment based on endoscopic evaluation. During the study, the SES-CD will be evaluated by both the Investigator and by a central reader blinded to study treatment. The SES-CD score from the central reader will be used to determine study eligibility:
    - Subjects with a SES-CD  $\geq 6$  at screening, or the ileum segmental SES-CD  $\geq 4$  at screening, will be eligible for study randomization;
    - Subjects will be randomized upon notification of the qualifying SES-CD.
  - For subjects who will be re-screened, endoscopies performed as part of the original screening period, within 30 days prior to the re-screen date, and reviewed by a central reader, may be used to determine eligibility.

## 6.2. Double-blind Treatment Period

The subject will begin study treatment upon confirmation of eligibility. For all subsequent visits in the Double-blind Treatment Period, an administrative window of  $\pm 3$  days is permitted. The following evaluations will be performed at the frequency specified in Table 3. The evaluations should be performed prior to dosing on the visit day, unless otherwise specified.

- Prior and concomitant procedures
- Prior and concomitant medications
- AE evaluation (continuously assessed)
- Electrocardiogram at the Week 12 and Week 52 Visits
- Contraception education (Section 6.5.6) at the Baseline Visit (Visit 2)
- A local urine pregnancy test will be performed on all FCBP. All local urine pregnancy test kits will be provided by the central laboratory. Urine and serum pregnancy tests should be performed if the FCBP has missed a menstrual period or the contraception method has changed at any time during the study.
- Vital signs and weight
- Complete physical examination (Section 6.5.1) at the Week 12 and Week 52 Visits
- Limited physical examination (Section 6.5.1) at the Baseline Visit, Week 24, and Week 36 Visits

- An abdominal examination to assess for the presence of an abdominal mass for the CDAI calculation will be performed at every visit. (Section 6.5.1)
- Clinical laboratory evaluations
- Subject Daily Diary Assessment
- CDAI assessment
  - Due to the delay in receiving the hematocrit sample results, beginning at the Week 12 Visit and thereafter until the Week 52 Visit, the CDAI score will be evaluated by the site using the hematocrit results from the previous visit.
- Ileocolonoscopy for SES-CD should be performed within the Visit window at Week 12 and Week 52.

[REDACTED]

- Dispense IP: The Principal Investigator (PI), Sub-investigator (Sub-I), or Study Coordinator (SC) should make an effort to witness subjects taking their first dose and record the date and time in the source document record. The IP (four tablets) should be taken QD by the subjects. Subjects will be instructed to take the IP in the morning, 30 minutes before breakfast, with a glass of water, and they will also be instructed to refer to the label for storage instructions.
- Return and count IP: A detailed record of the doses taken and doses missed between visits and at visits should be recorded in the Study Drug Record eCRF and the subject's source documents. Also, a record of the overall number of tablets dispensed and tablets returned at each visit must be maintained in the subject's source documents and recorded in the Drug Accountability eCRF.

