**Table 2: Study Endpoints**

| Endpoint  | Name                          | Description  | Timeframe |
|-----------|-------------------------------|--|-----------|
| Primary   | Efficacy (Clinical remission) | The proportion of subjects achieving clinical remission, defined as a CDAI score < 150, at Week 12 | Week 12   |
| Secondary | Efficacy                      | The proportion of subjects achieving clinical remission, defined as a CDAI score < 150, at Week 52 | Week 52   |

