### 6.5.3. Clinical Laboratory Assessments

Clinical laboratory evaluations will be performed by a central laboratory to include the following laboratory assessments performed at the frequency specified in [Table 3](#):

- Hematology panel will include: complete blood count (CBC) with differential, including red blood cell (RBC) count, hemoglobin, hematocrit, mean corpuscular hemoglobin (MCH), mean corpuscular hemoglobin concentration (MCHC), mean corpuscular volume (MCV), white blood cell (WBC) count (with differential), and platelet count.
- Serum chemistry panel will include: total protein, albumin, calcium, phosphorous, glucose, total cholesterol, triglycerides, uric acid, total bilirubin, alkaline phosphatase, aspartate aminotransferase (AST)/serum glutamic oxaloacetic transaminase (SGOT), alanine aminotransferase (ALT)/serum glutamic pyruvic transaminase (SGPT), sodium, potassium, chloride, carbon dioxide, blood urea nitrogen (BUN), creatinine, lactic dehydrogenase (LDH), magnesium, and complement activation (Bb, C3a and C5a).
- Coagulation assessment will include: prothrombin time (PT) and activated partial thromboplastin time (APTT)
- Urinalysis will be done at the central lab and will include specific gravity, pH, glucose, ketones, protein, blood, bilirubin, leukocyte esterase, nitrite, and urobilinogen. Microscopic urinalysis (bacteria, casts, crystals, epithelial cells, RBC, and WBC) will be performed only if the dipstick urinalysis is abnormal.

Clinical laboratory evaluations are not required to be fasting. However, the site will record whether a clinical laboratory evaluation was fasting or nonfasting on the lab requisition form.

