### 6.6.5. Ileocolonoscopy

All eligible subjects are required to have ileocolonoscopies performed during the Screening Period, Week 12, and Week 52. The screening ileocolonoscopy should be performed if the subject's screening CDAI score is  $\geq 220$  and  $\leq 450$ .

Subjects who discontinue from the study prior to the Week 52 Visit, will have the ileocolonoscopy done at the ET Visit, if an ileocolonoscopy has not been performed within 8 weeks of the previous ileocolonoscopy.

Video images of all endoscopic procedures will be captured and sent to a qualified centralized reader for calculation of the SES-CD to assess subject eligibility at screening, and to assess efficacy at Weeks 12 and 52. Additionally, the local SES-CD will be collected from the investigational sites. The site will receive a central reader SES-CD report during the Screening Period to determine if the SES-CD inclusion criterion is met.

For subjects at increased risk for colorectal cancer, pan-colonic surveillance with colonoscopy and biopsies should be done according to local guidelines.

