**Table 4: IP Dispensing Schedule: Double-blind Treatment Period**

| Week 0
Week 4
Week 8 | Week 12       | Week 16        | Week 20       | Week 24        | Week 28       | Week 32        | Week 36       | Week 40        | Week 44       | Week 48        |
|-------------------------------------|----------------------|-----------------------|----------------------|-----------------------|----------------------|-----------------------|----------------------|-----------------------|----------------------|-----------------------|
| GED-0301
160 mg QD               | Placebo
QD        | GED-0301
160 mg QD | Placebo
QD        | GED-0301
160 mg QD | Placebo
QD        | GED-0301
160 mg QD | Placebo
QD        | GED-0301
160 mg QD | Placebo
QD        | GED-0301
160 mg QD |
|                                     | Placebo
QD        | GED-0301
40 mg QD  | Placebo
QD        | GED-0301
40 mg QD  | Placebo
QD        | GED-0301
40 mg QD  | Placebo
QD        | GED-0301
40 mg QD  | Placebo
QD        | GED-0301
40 mg QD  |
|                                     | GED-0301
40 mg QD | GED-0301
40 mg QD  | GED-0301
40 mg QD | GED-0301
40 mg QD  | GED-0301
40 mg QD | GED-0301
40 mg QD  | GED-0301
40 mg QD | GED-0301
40 mg QD  | GED-0301
40 mg QD | GED-0301
40 mg QD  |
| Placebo
QD                       | Placebo
QD        | Placebo
QD         | Placebo
QD        | Placebo
QD         | Placebo
QD        | Placebo
QD         | Placebo
QD        | Placebo
QD         | Placebo
QD        | Placebo
QD         |

IP = investigational product; QD= once daily.

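### Does the previous-visit hematocrit rule leave the efficacy CDAI, and so the primary endpoint, undefined?

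*Protocol*

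**What the plan says.** The primary endpoint in Protocol Table 2 is "The proportion of subjects achieving clinical remission, defined as a CDAI score < 150, at Week 12". Clinical response at Week 12 and three Week 52 endpoints (remission, sustained remission, corticosteroid-free remission) rest on the same score.

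The hematocrit rule appears twice in the current protocol:

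- Section 6.2, under the CDAI assessment: from Week 12 until the Week 52 Visit, "the CDAI score will be evaluated by the site using the hematocrit results from the previous visit". The reason given is the delay in receiving the result.
- Table 3, footnote c, which deals with early escape: "beginning at the Week 12 Visit, and throughout the remainder of the study, the CDAI score will be evaluated by the site" in the same way.

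Section 6.6.2 and Appendix D call for a hematocrit value without naming the visit. Section 6.6.1 says that diary data are extracted from the electronic devices to calculate the CDAI efficacy parameters; it does not mention hematocrit. Table 3 schedules hematology at every visit, and Section 6.5.3 assigns it to the central laboratory: "Clinical laboratory evaluations will be performed by a central laboratory to include the following laboratory assessments performed at the frequency specified in" the Table of Events. The readable SAP gives no rule on hematocrit within the CDAI.

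**The concern.** From Week 12 on, the only readable instruction for the hematocrit item uses the older value. A programmer who took Section 6.2 as the rule for every CDAI would build the Week 12 endpoints from a hematocrit drawn about 4 weeks earlier, and under footnote c the Week 52 endpoints too. For the endoscopic score the protocol does keep two versions apart: the central read serves efficacy, and "Additionally, the local SES-CD will be collected from the investigational sites". Nothing readable does the same for the CDAI.

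Two features make this look more than cosmetic. Each hematocrit point carries 6 CDAI points, and remission is a hard cut. And under Table 4 both alternating regimens take placebo in Weeks 44-48 and active drug in Weeks 48-52, while the third regimen takes drug throughout. A lagged Week 52 score would then join a hematocrit from the end of a placebo block to symptoms from the end of an active block, in two of the three regimens only. At stake would be a diluted treatment comparison on the primary endpoint and several secondary ones.

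**Working it through.** **1. What the rule is for**

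- *Its reason.* Late laboratory results matter for a decision taken at the visit. An endpoint derived from the database can wait for them.
- *Its actor.* Both statements say the score is evaluated by the site.
- *Its start.* CDAI and hematology are also scheduled at Weeks 4 and 8, with the same laboratory, and no lag is applied there. The rule starts at Week 12, when early escape opens.
- *Its setting.* Footnote c gives it directly after the early-escape text.

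Together these describe an operational score. No readable passage makes it the endpoint score.

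**2. The two end points**

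Section 6.2 runs until the Week 52 Visit; footnote c runs through the rest of the study. If the first includes Week 52, the clear difference is the Follow-up CDAI, for which no readable efficacy endpoint exists. If it excludes Week 52, the difference reaches the site's Week 52 score. Footnote c itself opens with the Week 12 to Week 52 window, and Section 3.2 defines a subject's completion as reaching Week 52, so the first reading is the more natural.

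**3. Planned power, reproduced**

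Inputs from Protocol Table 5: remission 22% v 36%; 266 v 798 at Week 12; 266 v 266 at Week 52; 2-sided 0.05.

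Power = Φ[(|p1 − p2| − 1.96·s0)/s1], where s0 = √[p̄(1 − p̄)(1/n1 + 1/n2)] and s1 = √[p1(1 − p1)/n1 + p2(1 − p2)/n2].

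- Week 12: p̄ = 0.325, s0 = 0.0332, s1 = 0.0306, power 99.3% (stated 99%).
- Week 52: p̄ = 0.29, s0 = 0.0393, s1 = 0.0389, power 94.7% (stated 95%).

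**4. Suppose the lagged value did enter the endpoint**

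Assumptions not in the documents: normal CDAI with SD σ = 100 (range 80-120), and 4-week hematocrit change with SD τ = 1 to 2.5 points, independent of the same-visit CDAI. The weight of 6 is from Appendix D.

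*Random change, mean zero.* A same-visit rate p = Φ(z) becomes Φ(z·σ/√(σ² + 36τ²)). With σ = 100 and τ = 2.5 the denominator is √(10,000 + 225) = 101.1.

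- 22% becomes 22.25% and 36% becomes 36.15%, a difference of 13.9 points.
- Power is 99.2% at Week 12 and 94.3% at Week 52.
- For τ = 1 to 2.5 at σ = 100, between 1.4% and 3.5% of subjects change status at 22% remission, and 1.8% to 4.5% at 36%. They move in both directions and nearly cancel.

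*A rise of 1 point in every arm.* The lagged CDAI is 6 points too high everywhere: 36% becomes Φ(−0.3585 − 0.06) = 33.8% and 22% becomes Φ(−0.7722 − 0.06) = 20.3%. Power is 99.2% and 94.2%.

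*A rise on active drug only.*

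| Assumed rise | Active remission | Power, Week 12 | Power, Week 52 (one regimen) |
|---|---|---|---|
| 0.5 point | 34.9% | 98.3% | 91.1% |
| 1 point | 33.8% | 96.1% | 86.0% |

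For σ = 80 to 120 the 1-point row gives active remission of 33.2% to 34.1% and Week 52 power of 82.8% to 87.9%. The error works against the drug.

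**The case for a change.** The strongest case for a change is that the text leaves two derivations open for the primary endpoint and writes down only the lagged one, although the remedy would be a sentence and the data are already scheduled. It is true that no readable passage names the hematocrit visit for the analysed CDAI, and that the two statements of the rule end differently. Both observations stand.

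The step from there to a defect does not. Text is redacted directly after the CDAI items in Protocol Section 6.6.2, in SAP Section 5.2, around SAP Sections 11.2 and 11.3, and in the closing sections of the SAP. Those are natural places for such a derivation, and a gap left by redaction cannot be counted as missing from the plan.

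The endoscopic parallel is weak. There the two scores come from different readers of the same examination, so the plan has to say whose reading counts. Here both hematocrits come from the central laboratory, and the question is only which draw to use.

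The argument from Table 4 is fair as a mechanism, but it needs hematocrit to follow 4-week on and off blocks. Protocol Section 1.3.3 supports alternating dosing with the contrary observation that most subjects had prolonged improvement up to Week 12 after 2 weeks of dosing. The figures above apply a flat shift to one arm and do not model the alternation.

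**Conclusion.** The concern does not call for a change. The previous-visit rule reads as a site score for use at the visit. For the endpoint, an analyst with a same-visit central-laboratory hematocrit at Weeks 12 and 52 would sensibly use it. The differing end wording is a clerical slip; on the more natural reading it reaches no efficacy endpoint in the readable text.

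Even if the lagged value were analysed, hematocrit changes alike in all arms would leave power at about 99% (Week 12) and 94% (Week 52), on the assumed CDAI SD of 100 and hematocrit-change SD of up to 2.5 points. The fall to 86% at Week 52 depends wholly on an assumed active-only rise of 1 point in 4 weeks. These power figures also describe the original design. The SAP records early termination, restricts the denominators of binary endpoints (Section 11.2.2.1) and drops multiplicity adjustment (Section 11.1), so 266 per arm no longer describes the Week 52 analysis.

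No separate carry-forward rule for a missing hematocrit is needed. Protocol Section 9.6.1 and SAP Section 11.2.2.1 already treat subjects with insufficient data as nonresponders. The conclusion rests on reading the site rule as operational; the redacted text cannot be checked to confirm it.
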